4. LIST OF ABBREVIATIONS AND DEFINITIONS OF TERMS

Abbreviation or Specialist Term	Explanation
AE	adverse event
ACE	Angiotensin-converting enzyme
BP	blood pressure
CDC	Central Distribution Center
CNS	central nervous system
COPD	chronic obstructive pulmonary disease
Co-V	Coronavirus
CPAP	continuous positive airway pressure
CRF	case report form
CT	computed tomography
DBP	diastolic blood pressure
DIC	disseminated intravascular coagulation
DMC	Data Monitoring Committee
DNI	Do Not Intubate
DNR	Do Not Resuscitate
GCP	Good Clinical Practice
HR	heart rate
IBW	ideal body weight
ICF	informed consent form
ICH	International Conference of Harmonization
IEC	International Electrotechnical Commission
iNO	inhaled nitric oxide
ILD	Interstitial Lung Disease
IL-6	Interleukin - 6
IRB	Institutional Review Board
LVEF	left ventricular ejection fraction

Abbreviation or Specialist Term	Explanation
MEDDRA	Medical Dictionary for Regulatory Activities
mL	milliliter
N2	nitrogen
NO	nitric oxide
NIAID	National Institute of Allergy and Infectious Diseases
(NIV)	Non Invasive Ventilation
O2	oxygen
OSA	obstructive sleep apnea
PEEP	Positive End-Expiratory Pressure
PPE	personal protective equipment
ppm	parts per million
PH	pulmonary hypertension
RR	respiratory rate
RT-PCR	Reverse transcription polymerase chain reaction
SAE	serious adverse event
SpO2	oxygen saturation by pulse oximeter
SAR	serious adverse reaction
SARC	Sarcoidosis
SARS	Serious Acute Respiratory Syndrome
SUSAR	Suspected Unexpected Serious Adverse Reactions
USADE	Unanticipated Serious Adverse Device Effect
V/Q	Ventilation Perfusion

5. INTRODUCTION

No targeted therapeutic treatments for coronavirus (COVID-19) have been identified. Symptoms range from mild upper respiratory tract infection to severe pneumonia and death. Progression of end stage disease is unpredictable with high fatality rates in mechanically ventilated subjects as a result of multi-organ failure. Prevention of COVID-19 progression in spontaneously breathing subjects with mild to moderate disease may result in improved morbidity and mortality as well as limiting the burden to limited healthcare resources.

Inhaled nitric oxide (iNO) is a well-established safe and effective vasodilator and has been approved for the treatment of persistent pulmonary hypertension in neonates. Bellerophon is currently developing INOpulse for the treatment of chronic pulmonary hypertension (WHO Group 1, 3 and 5) with ongoing Phase 2 and Phase 3 studies in PH-ILD, PH-COPD and PH-SARC. The proprietary INOpulse® technology, utilizes high concentration pulses to ensure a precise and constant dose regardless of a subject's respiratory rate or inspiratory volume. The pulsatile technology allows dose titration, providing much higher doses/concentrations than currently available in hospital based systems, as well as reduces the overall size of the therapy, allowing it to be administered at home. Also as a result of the pulsatile technology, iNO is delivered during the first half of each inspiration and therefore, does not increase the risk of exposure to aerosolized virus during iNO administration.

The pathobiology of COVID-19 infection may provide a rationale for the mechanism of the severe hypoxemia. The virus enters the pneumocyte via the ACE2 receptor resulting in inflammation and causing lung injury. As the virus gains access to the systemic circulation it can enter the endothelial cells where the ACE2 receptor is widely expressed on the cell surface resulting in an endotheliitis and which can potentially involve multiple organs (Varga, 2020). This inflammatory process, causing endothelial dysfunction, shifts the endothelium toward a more vasoconstrictive, procoagulant state. This endothelial dysfunction could potentially lead to pulmonary vasoconstriction with resultant ventilation perfusion (V/Q) mismatch in the lung. Inhaled nitric oxide (iNO) has the potential to optimize V/Q matching by dilating the blood vessels in the least affected areas of the lung. In addition, nitric oxide has an important role in the immune response and has been demonstrated to inhibit the replication of SARS-CoV (Akerstrom, 2005; Keyaerts, 2004) with evidence also supporting a clinical benefit in subjects with SARS (Akerstrom, 2005; Chen, 2004). SARS-CoV-2, the pathogen responsible for COVID-19, shares 79.5% of its genomic sequence with SARS-CoV (Guo, 2020). It is therefore postulated that iNO might have dual beneficial effects in COVID-19 subjects.

The clinical spectrum of the COVID-19 infection ranges from mild signs of upper respiratory tract infection to severe pneumonia and death. Currently, the probability of progression to end stage disease is not well understood, however, preventing progression in subjects with mild or moderate disease would improve morbidity/mortality and reduce the impact on limited healthcare resources. Furthermore, reducing the need for positive pressure ventilator support as observed in the Chen study (2004) may limit lung damage. Based on the genomic similarities between the two coronaviruses, the data in SARS-CoV supports the potential for iNO to provide benefit for subjects infected with COVID-19. Exogenous iNO in subjects who have mild to moderate COVID-19 could prevent further deterioration and potentially improve the time to recovery.

INOpulse therapy using iNO125 (125 mcg/kg IBW/hr) was authorized for treatment of COVID-19 via FDA's Intermediate Expanded Access Program in March 2020. Eligible patients were COVID-19 positive by RT-PCR, or with high suspicion of infection, and receiving supplemental oxygen at no more than 10 L/min. Data from the first 25 patients treated with INOpulse for COVID-19 was conducted in April 2020, and demonstrated INOpulse was well tolerated with no increase in methemoglobin levels above 1.5%. Of the 22 COVID-19 positive patients to complete treatment with INOpulse, 19 completed treatment without deterioration (86%) with 3 showing signs of deterioration (1 death and 2 intubated). The median time for INOpulse treatment was 4 days and the median time from start of INOpulse treatment to hospital discharge was 6 days.

6. OBJECTIVES

6.1 Primary Objective

The primary objective in this study is to verify the efficacy of INOpulse in subjects with COVID-19.

6.2 Secondary Objective:

The secondary objective in this study is to evaluate the safety of INOpulse in subjects with COVID-19.

7. ENDPOINTS

7.1. Primary Endpoint

Proportion of subjects who died or had respiratory failure through Day 28.

Respiratory failure is defined as one of:

- Endotracheal intubation and mechanical ventilation
- Extracorporeal membrane oxygenation
- High-flow nasal cannula oxygen delivery (i.e., reinforced nasal cannula delivering heated, humidified oxygen with fraction of delivered oxygen ≥ 0.5 and flow rates of ≥ 30 l/min)
- Noninvasive positive pressure ventilation
- Clinical diagnosis of respiratory failure with initiation of none of these measures only when clinical decision-making is driven solely by resource limitation or in the event the subject is not intubated due to (DNI) or do not resuscitate (DNR) status

7.2. Secondary Endpoints

1. 8-point NIAID ordinal scale assessed at Day 7, 14, 28 and day of discharge (Table 1)
2. Proportion of subjects to recover, defined as return to room air or baseline oxygen requirements, or discharged alive from hospital [Through Day 28]
3. Proportion of subjects discharged alive from hospital [Through Day 28]
4. Duration of hospitalization [Through Day 28]
5. Mortality [Through Day 28]
 - All-cause mortality
 - Cardiopulmonary mortality
6. Proportion of subjects with a negative conversion of RT-PCR from a nasopharyngeal or bilateral nasal swab [Through Day 28]

7.3. Safety Endpoint

Proportion of subjects with adverse events leading to study drug discontinuation [Through Day 28]

7.4. Overall Study Design

This is a randomized, double-blind, placebo-controlled study to assess the efficacy and safety of pulsed iNO compared to placebo in subjects with COVID-19 who are hospitalized and require supplemental oxygen without assisted ventilation. Prior to receiving treatment with INOpulse, subjects will be screened to confirm eligibility. All subjects (ie, both active and placebo) should be offered current standard of care for treatment of COVID-19. COVID-19 infection must be confirmed via positive RT-PCR, or have high index of suspicion of infection with results pending. Upon successful completion of screening, subjects will be randomized to receive placebo or iNO125 mcg/kg IBW/hr 24 hours daily until resolution of hypoxemia, protocol

defined respiratory failure, hospital discharge or Day 28, whichever occurs first. In instances where continuous INOpulse dosing is not feasible (eg, due to PPE limitations), INOpulse should be used a minimum of 12 hours daily. Subjects will be followed through 30 days after discontinuation of INOpulse therapy to assess their clinical status.

7.5. Treatment Assignment

Subjects will be randomized and stratified for the use of Remdesivir for the treatment of COVID-19. In addition randomization will be stratified by: oxygen flow rate, NT-proBNP and comorbidities (diabetes, hypertension, cardiovascular disease [including ischemic heart disease, heart failure, cerebrovascular disease, peripheral vascular disease] and obesity [BMI ≥ 30]).

8. STUDY POPULATION

8.1. Number of Subjects to be Studied

Approximately 500 subjects will be randomized.

8.2. Inclusion Criteria

Subjects must meet all of the following inclusion criteria to be enrolled and eligible to participate in the study:

1. Signed Informed Consent Form (and assent as appropriate) prior to the initiation of any study mandated procedures or assessments.
2. At least 18 years old
3. [REMOVED IN AMENDMENT #1]
4. Subject must be hospitalized and have the following:
 - proven or high suspicion of SARS-CoV-2 infection, and
 - requiring oxygen supplementation defined as:
 - $\text{SpO}_2 \leq 92\%$ regardless of supplemental oxygen (ie on room air or on oxygen); or
 - $\text{SpO}_2 \geq 92\%$ on supplemental O₂ and in the opinion of the Investigator it is not safe to decrease or remove the supplemental oxygen
 - require supplemental oxygen of no more than 10 L/minute, and
 - radiologic suspicion or proof of COVID-19 pneumonitis (chest x-ray or CT scan)
5. Female subjects of childbearing potential must have a negative pre-treatment pregnancy test (serum or urine). All female subjects should take adequate precaution to avoid pregnancy.
6. Willing and able to comply with treatment schedule and study procedures.

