- Review of prior and concomitant medications, that includes all current COVID-19 treatments (all therapies prescribed for the treatment of COVID-19)

On the day of Randomization (Day 0):

- Review inclusion and exclusion eligibility criteria
- Review of prior and concomitant medications, that includes all current COVID-19 treatments (all therapies prescribed for the treatment of COVID-19)
- Electrocardiogram (ECG)
- Vital signs (heart rate, respiratory rate, blood pressure, temperature)
- Oxygen saturations
- Document oxygen flow requirements

- Upon initiating INOpulse, methemoglobin should be < 3% and SpO2 > 89% (with supplemental oxygen if required) prior to continuing with treatment. Methemoglobin will be monitored prior, during the 1st hour (every ½ hour), and approximately 4-5 hours after initiation of INOpulse therapy.
- Adverse event(s) assessment

Daily assessments while on INOpulse and hospitalized (up to Day 27) will be performed as follows:

- Review of prior and concomitant medications, that includes all current COVID-19 treatments (all therapies prescribed for the treatment of COVID-19)
- Oxygen flow requirements
- While hospitalized and on INOpulse, vital signs (heart rate, respiratory rate, blood pressure, temperature), SpO2 via pulse oximetry and methemoglobin will be measured **twice daily** to minimize exposure to healthcare professionals
 - In the event an increase in oxygen flow rate is clinically indicated, vital signs and SpO2 should be monitored every 6 hours until stabilized.
- Adverse event(s) assessment
- Respiratory Failure status
- Clinical status using an 8-point NIAID ordinal scale ([Table 1](#))

At **End of Treatment** (INOpulse discontinuation), the following assessments will be completed:

- CBC with differential, chemistry panel (sodium, potassium, chloride, CO2, BUN, creatinine, glucose), LFTs (AST/ALT and total bilirubin), triglycerides, troponin (High Sensitivity Cardiac Troponin [HS-cTN], procalcitonin, ferritin, fibrinogen, D-dimer, NT-proBNP and LDH. If available locally, CRP, Von Willebrands Factor, Factor VIII Activity, Protein C, Protein S, Homocysteine, Antithrombin 3, Thrombelastography (TEG), G6PD deficiency and Prothrombin gene G2021A
- COVID-19 RT-PCR obtained by nasopharyngeal or bilateral nasal swab
- Review of prior and concomitant medications, that includes all current COVID-19 treatments (all therapies prescribed for the treatment of COVID-19)
- Electrocardiogram (ECG)

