10.1.7. Vital Sign Measurements

Vital sign measurements will include heart rate (HR), respiratory rate (RR), blood pressure (BP, systolic and diastolic), and temperature. Oxygen flow rate and any changes to flow rate will be documented. SpO₂ will also be documented and monitored to ensure levels remain >80% during the study and >89% upon initiation of treatment on Day 0.

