10.0 Conventions and Derivations

The primary endpoint is the proportion of subjects who died or had respiratory failure (DRF) through day 28 (treatment day 27), where respiratory failure is defined as one of the following:

- Endotracheal intubation and mechanical ventilation;
- Extracorporeal membrane oxygenation;
- High-flow nasal cannula oxygen delivery (i.e., reinforced nasal cannula delivering heated, humidified oxygen with fraction of delivered oxygen ≥ 0.5 and flow rates of ≥ 30 l/min);
- Noninvasive positive pressure ventilation;
- Clinical diagnosis of respiratory failure with initiation of none of these measures only when clinical decision-making is driven solely by resource limitation or in the event the subject is not intubated due to do not intubate (DNI) or do not resuscitate (DNR) status.

Duration of therapy will be calculated as the date of first dose of study drug on the INOpulse Usage Form through the date of last dose of study drug on the End of Treatment CRF page.

Baseline is defined as the last assessment prior to the first dose of study drug.

Body Mass Index is defined as subject weight (kg) divided by height (m²).

The age at COVID-19 diagnosis is defined as the number of years from the date of birth to the date of diagnosis of COVID-19, which will be derived based on the table below. No imputation will be done for missing disease diagnosis date (Year, Month, Day). The age calculation will be truncated to a whole number.

Table 3: Calculation for Age at COVID-19 Diagnosis

Observed Portion	Missing Portion	Formula to Calculate Duration
Year, Month, Day		(Date of Diagnosis – Date of Birth + 1)/365.25
Year, Month	Day	[Year (Date of Diagnosis) – Year (Date of Birth)] + [Month (Date of Diagnosis) – Month (Date of Birth)]/12
Year	Month, Day	[Year (Date of Diagnosis) – Year (Date of Birth)]

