13.5.5.2 Subject Recovery

The proportion of subjects to recover, defined as return to room air or baseline oxygen requirements, or discharged alive from the hospital, through day 28, will be summarized using descriptive statistics (totals and percentages) for subjects overall and by treatment group. The estimand of the proportion of recovery/discharge will be calculated by treatment group, along with 95% confidence intervals. A chi-square test will be used to test the significance in the proportion of subjects who recovered between the INOpulse and placebo treatment groups.

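### Recovery has no SpO2 condition and uses a pre-dose baseline, so a subject can count as recovered while still meeting the trial's own entry definition of requiring oxygen

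*Protocol*

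**What the plan says.** - **Entry.** Protocol 8.2 item 4 (repeated in the Synopsis) defines the need for oxygen in two ways. One is SpO2 of 92% or less, "regardless of supplemental oxygen (ie on room air or on oxygen". The other is SpO2 of 92% or more on oxygen that the investigator judges unsafe to reduce or remove. A further line, "require supplemental oxygen of no more than 10 L/minute, and", sets a ceiling on flow but no minimum.
- **Recovery.** Protocol 7.2 item 2 has it "defined as return to room air or baseline oxygen requirements, or discharged alive from hospital". SAP 13.5.5.2 repeats this: "defined as return to room air or baseline oxygen requirements, or discharged alive from the hospital, through day 28". Neither gives a saturation condition, a minimum duration, or a rule for subjects already on room air at entry.
- **Baseline.** SAP 10.0: "Baseline is defined as the last assessment prior to the first dose of study drug".
- **SpO2 elsewhere.** The Synopsis asks at initiation for "SpO2 > 89% (with supplemental oxygen if required) prior to continuing with treatment". Protocol 10.1.7 has SpO2 "monitored to ensure levels remain >80% during the study and >89% upon initiation of treatment on Day 0". These are monitoring levels and are not linked to recovery. Treatment ends on resolution of hypoxemia, but that term has no SpO2 definition and is not linked to recovery either.
- **Testing.** Recovery is compared by chi-square test and is the second secondary endpoint in the fixed sequence of SAP 13.5.2, after the NIAID score.

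**The concern.** The same bedside state, an inpatient on room air with SpO2 of 90–92%, can be the qualifying condition at entry and a success afterwards. Such subjects add successes that do not reflect resolution of the condition that brought them into the trial. If they occur about equally in both arms, they pull the arms together.

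Recovery is formally tested. If the sequence reaches it and it fails, SAP 13.5.2 stops testing of discharge, hospital duration, mortality and RT-PCR conversion.

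**Working it through.** The documents state no recovery rate, power or sample size for this endpoint, so there is no plan figure to reproduce. The check is a comparison of definitions, followed by an illustration on assumed rates.

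**1. Subject enrolled on room air at SpO2 91% who stays there.**
- Entry: 91% is at or below 92%, and room air is named as an admissible state. The subject meets the SpO2 condition.
- Start of treatment: 91% exceeds 89%, and the Synopsis asks for oxygen only if required. Dosing can proceed.
- Baseline limb: the last pre-dose assessment shows no oxygen use, so unchanged status equals baseline oxygen requirements. The limb is met at the first post-dose assessment.
- Room-air limb: unclear, because the text speaks of a return to room air and this subject never left it.
- Later course: recovery is counted through Day 28 with no requirement that it last. Later deterioration or death does not reverse it.

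**2. Subject weaned from oxygen to room air at SpO2 91%.** The room-air limb is met on its plain wording. The first part of the entry definition of requiring oxygen is met as well.

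**3. Size.** The inputs are 250 per arm (500 subjects, 1:1) and two-sided 5%, from SAP 8.1. The recovery rates and the share f are assumptions. Let f be the share of each arm counted automatically, d_o the treatment difference in the other subjects, and d_a the difference the affected subjects would show under a definition that respects the entry condition.

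- Intended difference: (1 − f)·d_o + f·d_a
- Counted difference: (1 − f)·d_o, because the affected subjects score 100% in both arms
- Loss: f·d_a

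If d_a = d_o, the counted difference is exactly (1 − f) times the intended one. If d_a is smaller than d_o, the loss is smaller.

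Largest case considered, d_a = d_o = 10 points. The counted rate in each arm is p′ = f + (1 − f)p, with power from the pooled two-proportion normal formula:

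| f | Counted difference | Power, 80% vs 90% | Power, 75% vs 85% |
|---|---|---|---|
| 0% | 10.0 points | 88% | 80% |
| 5% | 9.5 points | 86% | 77% |
| 10% | 9.0 points | 84% | 75% |
| 20% | 8.0 points | 79% | 69% |

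Example for 80% vs 90% at f = 20%: 0.20 + 0.80 × 0.80 = 84% and 0.20 + 0.80 × 0.90 = 92%, a difference of 8 points.

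Milder case: the affected subjects would truly recover at 97% vs 99% (d_a = 2 points), with f = 10%. The intended difference is 0.9 × 10 + 0.1 × 2 = 9.2 points and the counted one is 9.0, a loss of 0.2 points.

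**The case against.** **The wording is a return to room air, not presence on it.** A reader might infer that every room-air entrant is an automatic success through that limb from the first assessment. The text does not support this: read strictly, the limb leaves them unclassified. Their success comes through the baseline limb and rests on SAP 10.0. The point about subjects weaned at low saturation does not depend on this reading.

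**The trial is meant for subjects receiving oxygen.** The study design describes subjects who require supplemental oxygen, and SAP 13.5.4 states that all score 4 at entry. Table 2 footnote 3 and Protocol 10.1.12 word the initiation rule as though oxygen is required, unlike the Synopsis. This suggests that room-air entry is uncommon. It does not rule it out, because inclusion 4 names room air and nothing enforces the score-4 statement.

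**Most affected subjects would succeed anyway.** This largely stands. Discharge alive also counts as recovery through Day 28. In the small, uncontrolled expanded-access series, median time from treatment start to discharge was 6 days. A reader might infer from the table above that the endpoint loses about 10 points of power or cannot be interpreted. The documents do not support that: f is unknown, and those figures assume that the affected subjects recover at the same rates as everyone else.

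**Defining recovery by oxygen support is a legitimate choice.** So it is. The difficulty here is that the trial's own entry rule defines need by saturation, including on room air, and the two definitions then overlap.

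**Conclusion.** The entry, baseline and recovery definitions conflict. A room-air entrant can be scored as recovered without change through the baseline limb, and a subject weaned at SpO2 of 92% or less is scored as recovered while still meeting the entry definition.

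The number affected is not given and is probably small. Dilution is at most a factor (1 − f) on the difference, assuming that the affected share is equal in the two arms and that these subjects would not benefit more than others. It may be close to nil if nearly all of them are discharged alive.

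The primary endpoint of death or respiratory failure is not affected. Recovery is tested only if both the primary endpoint and the NIAID analysis are significant. This is a modest but real defect in a formally tested secondary endpoint, and cheap to remove.

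**What to change.** Reconcile Protocol 7.2 item 2 and 8.2 item 4 with SAP 9.0, 10.0 and 13.5.5.2:

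1. State that neither oxygen limb, room air or baseline oxygen requirements, can be met while the subject still meets inclusion 4's definition of requiring oxygen. Adding a saturation condition to the room-air limb alone would not be enough, because a room-air entrant would still pass through the baseline limb.
2. State that baseline oxygen requirements means the pre-illness requirement, not the SAP 10.0 pre-dose value. This also prevents a subject on unchanged study-entry oxygen from counting as recovered.
3. State that subjects on room air at entry recover only when the entry condition is no longer met, or on discharge alive.

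Use the SpO2 already recorded twice daily on INOpulse and at End of Treatment. Table 2 does not mark SpO2 for inpatients off INOpulse. Recording it there is optional; if it is not added, the SAP should say which reading is used for them.

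The cost is wording in both documents and a slightly lower reported recovery rate in both arms. Subjects with chronically low saturation would count only at discharge. The same would hold for subjects on long-term oxygen who still meet the second part of inclusion 4, unless the text makes an exception for them.
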